1.4 BENEFIT/RISK

ACP-196 is a potent, orally available small-molecule inhibitor of Btk. A PK/PD study has been completed with ACP-196 in healthy volunteers (ACE-HV-001; Section1.3.1). The safety results showed no identified safety risks in healthy subjects receiving 1 or 2 days of ACP-196 \leq 100 mg. In study ACE-CL-001, a study of ACP-196 in subjects with relapsed/refractory or previously untreated CLL or Richter's syndrome, no DLTs have been reported at dosages of \leq 400 mg QD or 100 and 200 mg BID. The overall response rate in the evaluable subjects for this study is currently 94% with some subjects obtaining PRs after only 2 cycles of therapy. Based on these robust results in subjects with CLL, the evaluation of ACP-196 in subjects with relapsed or refractory MM is warranted.

1.5 SUMMARY AND CONCLUSIONS

This study comprises a pilot evaluation of the safety and activity of the potent, secondgeneration Btk inhibitor, ACP-196, in patients with relapsed or refractory MM. The design and conduct of this study is supported by an understanding of the natural history and current therapies for subjects with lymphoid cancers; knowledge of the efficacy and safety of the first-generation BCR inhibitor (eg, ibrutinib) in subjects with hematologic cancers; and the available nonclinical and clinical information regarding ACP-196. Preclinical studies are ongoing in parallel to identify biomarkers that may be evaluated in this clinical trial as correlates of response to Btk-directed therapy and that may permit selection of patients who are particularly likely to benefit from ACP-196 treatment for MM.

2.0 STUDY OBJECTIVES

2.1 PRIMARY OBJECTIVE

• To characterize the safety profile of ACP-196 with and without dexamethasone in subjects with relapsed or refractory MM

2.2 SECONDARY OBJECTIVES:

- To characterize the PK profile of ACP-196 with and without dexamethasone and the PK profile of dexamethasone with concomitant ACP-196 administration
- To evaluate the PD effects of ACP-196 with and without dexamethasone
- To evaluate the activity of ACP-196 with and without dexamethasone as measured by overall response rate, duration of response, clinical benefit rate, disease control rate, and progression-free survival
- To explore the relationship between biological markers in MM cells and response to therapy

3.0 STUDY DESIGN

3.1 DESCRIPTION OF STUDY

This study is a multicenter, open-label, randomized, parallel-group study to be conducted at approximately 20 sites in 2 countries (United Kingdom and United States). Forty subjects will be randomized 1:1 into the following 2 cohorts to receive ACP-196, with and without dexamethasone:

- Cohort 1: ACP-196 100 mg BID continuously
- Cohort 2: ACP-196 100 mg BID continuously and 40 mg dexamethasone once weekly

Twenty-eight days of study drug administration is 1 cycle. Treatment may be continued for > 28 days until disease progression or an unacceptable drug-related toxicity occurs. For subjects in Cohort 1, if documented disease progression occurs, then dexamethasone can be added to the treatment regimen. Additional dose modification provisions are provided in Section 3.5.5. Note: temporary withholding of study drug for as little as 7 days can cause a transient worsening of disease and/or of constitutional symptoms. Refer to Section 3.8 for more information on assessing disease progression under these circumstances. All subjects who discontinue study drug will have a safety follow-up visit 30 (±7) days after the last dose of study drug unless they have started another cancer therapy within that timeframe.

All subjects will have standard hematology, chemistry, and urinalysis safety panels performed at screening. Once dosing commences (Day 1), all subjects will be evaluated for safety, including serum chemistry and hematology, once weekly for the first 4 weeks, every 2 weeks in Cycle 2 and monthly thereafter. PK/PD testing will be done in Cycle 1 and Cycle 2. Tumor assessments will be done at 8- to 12-week intervals during the trial.

Refer to Appendix 5 for a comprehensive list of study assessments and their timing. The end of trial is defined as the point when the last subject on the study exits the study for any reason.

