4.1.4 Concomitant Medications and Therapy

All concomitant medications and procedures from within 21 days before the start of study drug administration through 30 days after the last dose of study drug should be documented.

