4.3 EARLY TERMINATION/SAFETY FOLLOW-UP VISIT

An early termination visit is required for any subjects who permanently discontinue study drug early for any reason including disease progression. Each subject should be followed for 30 (±7) days after his or her last dose of study drug (ie, the "safety follow-up visit") to monitor for resolution or progression of AEs (see Section 6.2.5) and to document the occurrence of any new events; unless, the subject receives a new anticancer therapy within this timeframe. Subjects who withdraw consent should still be encouraged to complete the safety follow-up assessments, but these assessments cannot be mandated once consent is withdrawn. The Schedule of Assessments (Appendix 5) describes the procedures required for the safety follow-up.

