6.2.1 Adverse Event Reporting Period

The AE reporting period for this study begins when the subject receives the first dose of study medication and ends with the safety follow-up visit (or last on-treatment visit if the safety follow-up visit is not done), or when the subject receives a new anticancer therapy. An exception to this reporting period is any AE occurring due to a protocol-defined screening procedure. Fatal AEs occurring within 30 days after the last dose of ACP-196 *AND* assessed by the investigator as related to ACP-196 must be reported as a SAEs.

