### 10.6 Analyses of Safety Endpoints

Safety analyses will be performed on All-treated population by treatment cohort.

Analyses of adverse events (AEs) will be performed on treatment-emergent AE (TEAE) data, unless otherwise specified. TEAEs are defined as those events with onset or

worsen date on or after the date of first dose of acalabrutinib, through the treatment phase to last dose of acalabrutinib, and within 30 days following the last dose of acalabrutinib, whichever is later. Common Terminology Criteria for Adverse Events (CTCAE) Version 4.03 or higher is used for AE grading.

Treatment-emergent AEs will be summarized in 3 groups: (1) acalabrutinib monotherapy, (2) acalabrutinib + dexamethasone, and (3) crossover from monotherapy to acalabrutinib + dexamethasone therapy. By this grouping method, AEs among subjects assigned to acalabrutinib monotherapy will be reported in group 1 when AEs occurred before crossover, and AEs occurred on/after crossover will be reported in group 3. Treatment-emergent AEs occurred on or after crossover will be summarized in the crossover group. Treatment-emergent AEs occurred before crossover will be summarized in the monotherapy group. All AE terms will be coded by Medical Dictionary for Regulatory Activities (MedDRA) Version 19.1 and will be presented by system organ class (SOC) and preferred term (PT). Treatment-emergent AEs will be summarized by SOC and PT and by CTCAE toxicity grade. The drug-related AEs, serious adverse events (SAEs) and drug-related SAEs, AEs leading to treatment discontinuation, dose delay and dose modification will be summarized by PT by CTCAE toxicity grade.

Death will be reported in a listing and summarized. A table will be provided for grade 5 AE and the relationship with any study drug.

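### AE reporting closes at a safety follow-up visit that may fall on day 23, but the SAP counts TEAEs to day 30, so up to 7 post-dose days carry no general AE reporting duty

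*Protocol*

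**What the plan says.** **Visit timing.** Protocol 3.1 plans a "safety follow-up visit 30 (±7) days after the last dose of study drug", waived for a subject who begins other cancer treatment in the meantime. Section 4.3 gives the same window: "Each subject should be followed for 30 (±7) days after his or her last dose of study drug". The synopsis, Appendix 5 footnote c and SAP 3.1 agree.

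**End of AE collection.** Protocol 6.2.1 says the AE reporting period "ends with the safety follow-up visit (or last on-treatment visit if the safety follow-up visit is not done"), and names a second closing event: "or when the subject receives a new anticancer therapy". One class of event has a fixed limit instead: "Fatal AEs occurring within 30 days after the last dose of ACP-196", if the investigator also judges them related, must be reported as SAEs.

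**Analysis window.** SAP 10.6 counts as treatment-emergent any event that starts or worsens from the first dose and "within 30 days following the last dose of acalabrutinib, whichever is later". The AE date-imputation rules in SAP 14.2.1 use the same boundary of last dose plus 30 days.

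**Neighbouring rules.** Protocol 4.1.4 ties concomitant medications to a fixed day, not to the visit: they are collected "through 30 days after the last dose of study drug should be documented". For laboratory, vital-sign and ECOG data, SAP 10.6.2 to 10.6.4 run to the later of 30 days after last dose and the date of the safety follow-up visit.

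**The concern.** A ± window around a visit is ordinary scheduling. The difficulty is that a movable visit closes AE collection while the reporting tables use a fixed day. A subject seen early, with every instruction followed, has AE and SAE reporting closed before the window that the TEAE tables describe has ended. A medication started on day 27 must be documented, but the AE that prompted it need not be.

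Safety is the primary objective. Treatment runs until progression or unacceptable toxicity, so the weeks after stopping are informative. The cohorts are small: forty subjects were planned in all, and SAP 3.1 records that enrollment was stopped early. A few uncollected events could change a cohort's percentage, and no choice of analysis set or table can recover events that were never collected.

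**Working it through.** The plan states no figure for this, so there is none to reproduce. The check is day arithmetic on the current text.

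**Inputs**
- Visit window: day 30 ± 7 after last dose (Protocol 3.1, 4.3).
- End of AE reporting: the visit itself (Protocol 6.2.1).
- End of TEAE window: day 30 after last acalabrutinib dose (SAP 10.6).
- Simplification: the last dose of study drug and the last dose of acalabrutinib fall on the same day. If dexamethasone continued longer and the visit were timed from it, the gap would be smaller.

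**Formulas**
- Earliest visit = 30 − 7 = day 23; latest = 30 + 7 = day 37.
- TEAE days with no general AE duty = max(0, 30 − visit day).
- Days collected but outside the TEAE window = max(0, visit day − 30).

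| Visit day | TEAE days not covered | Share of 30 days | Collected beyond TEAE window |
|---|---|---|---|
| 23 | 7 | 23.3% | 0 |
| 24 | 6 | 20.0% | 0 |
| 25 | 5 | 16.7% | 0 |
| 26 | 4 | 13.3% | 0 |
| 27 | 3 | 10.0% | 0 |
| 28 | 2 | 6.7% | 0 |
| 29 | 1 | 3.3% | 0 |
| 30 | 0 | 0% | 0 |
| 31 to 37 | 0 | 0% | 1 to 7 |

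**Is there another duty that fills the gap?**
- Protocol 4.1.3 says when AE recording starts but gives no end; 6.2.1 supplies the end.
- Section 6.2.5 follows up only events met during the reporting period, so it does not bring in new ones.
- No section requires an AE contact at day 30 after an early visit.
- The one AE rule fixed at 30 days covers fatal events judged related to ACP-196. Non-fatal SAEs, and deaths judged unrelated, are outside it.

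**When the visit does not take place.** Reporting then ends at the last on-treatment visit, so the uncovered part can approach all 30 days. New anticancer therapy also ends reporting. The SAP's TEAE definition does not shorten the window in either case.

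**Illustration only.** If visits were spread equally over whole days 23 to 37 (an assumption), 7 of 15 would be early. The total shortfall is 7+6+5+4+3+2+1 = 28 days, which is 28/15 = 1.87 days per subject, or 1.87/30 = 6.2% of the post-dose window. The documents give no actual distribution of visit days.

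**The case against.** The strongest reply is that the gap is narrow. Several duties run to day 30 whatever the visit date: concomitant medications and procedures (4.1.4), fatal AEs judged related (6.2.1), and pregnancies by date of conception (6.2.3). AEs already open are followed to resolution or stability (6.2.5). This stands. What is uncovered is new-onset events other than related fatal AEs.

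The 23% is also a worst case, measured against the post-dose tail alone. Against the whole TEAE window it is less: with an assumed 56 days on treatment, 7/(56 + 30) = 8%. The SAP plans subject-incidence tables, not exposure-adjusted rates, so a repeat of a term already reported at the same or higher grade changes no count. The study is descriptive, with no formal hypothesis test (SAP 5). These points limit the importance of the gap but do not close it.

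Two stronger readings are tempting. A reader might infer that nothing is observed on days 24 to 30; the duties just listed show otherwise, and a site may report events unprompted. A reader might also infer that death counts are understated. That is possible but not shown: SAP 10.6 lists and summarizes deaths without stating a TEAE-window limit, and death from any cause is a PFS event.

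Finally, removing the minus side of the visit window looks like the obvious repair, but it could lose data. The visit is waived once other cancer therapy starts. A subject starting such therapy on day 26 could no longer be seen on days 23 to 25, and reporting might fall back to the last on-treatment visit. The Amendment 1 rationale expects subjects who progress to change regimen quickly, so this case deserves weight.

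**Conclusion.** The mismatch is real on the current text: an on-protocol visit can close AE reporting up to 7 days before the TEAE window ends, and a visit not done can close it earlier still. Late-onset TEAEs may be under-collected. The 7-day maximum is exact when the visit takes place within its window and both clocks start from the same last dose. The number of missed events cannot be estimated, because it depends on visit days and late-onset event rates that the documents do not give. This is a cheap improvement to the data for the primary objective. It is not evidence that the safety results are materially wrong.

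**What to change.** Keep the ±7-day visit window. Amend Protocol 6.2.1 so that AE and SAE reporting runs to the later of day 30 after last dose and the safety follow-up visit, or to the start of new anticancer therapy if that is earlier. Add a telephone contact at day 30 when the visit was earlier or was not done. This matches the rule the SAP already applies to laboratory, vital-sign and ECOG data.

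Subjects who start new therapy before day 30 will still have collection stop short of the SAP window. For them, and for subjects already past follow-up, the clinical study report can state how many had AE collection end before day 30.

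The cost is a wording change, an occasional telephone call and one line in the report.

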3.2 STUDY PARAMETERS

3.2.1 Safety Parameters

The safety of ACP-196 with and without dexamethasone will be characterized by the type, frequency, severity, timing of onset, duration, and relationship to study drug (ie, ACP-196, dexamethasone, or both) of any treatment-emergent AEs or abnormalities of laboratory tests; serious adverse events (SAEs); or AEs leading to discontinuation or dose reduction of study treatment.

For consistency of interpretation, AEs will be coded using the Medical Dictionary for Regulatory Activities (MedDRA), and the severity of AEs and laboratory abnormalities will be graded using the Common Terminology Criteria for Adverse Events (CTCAE), Version 4.03. Standard definitions for seriousness will be applied (see Section 6.1).

3.2.2 Efficacy Parameters

Standardized response and progression criteria have been established for MM (Rajkumar 2011); assessments of ACP-196 efficacy in this study will be based on these criteria. Efficacy endpoints will include:

- Overall response rate (ORR)
- Duration of response
- Clinical benefit rate
- Disease control rate

• Progression-free survival

3.2.3 Pharmacokinetic and Pharmacodynamic Parameters

Standard PK parameters for ACP-196 and dexamethasone in plasma will be evaluated in this study. A full description of the PK parameters is provided in Section 5.5.4.

The occupancy of Btk by ACP-196 will be measured in peripheral blood mononuclear cells (PBMCs) and bone marrow, when available, with the aid of a biotin-tagged ACP-196 analogue probe. The effect of ACP-196 on biologic markers of B-cell function will also be evaluated.

3.3 RATIONALE FOR STUDY DESIGN AND DOSING REGIMEN

As described in Section 1.3, preliminary data from the ongoing Phase 1/2 study in subjects with relapsed/refractory or previously untreated CLL have shown that ACP-196 is well tolerated at dosages of 100 to 400 mg QD and 100 to 200 mg BID. In addition, preliminary PD data from ACE-CL-001 show that Btk occupancy with ACP-196, in peripheral blood, is > 95% at 4 hours after QD dosing but decreases to < 95% at 24 hours with QD dosing, while with BID dosing complete Btk occupancy (95% to 99%) is maintained over 24 hours at steady state (Table 1-3). These data suggest that de novo synthesis of Btk can occur within 24 hours in peripheral blood cells. BID dosing may ensure Btk inhibition for the entire 24 hours and thus may be beneficial in terms of increasing efficacy and/or decreasing development of resistance to ACP-196. In addition, having information regarding the safety and pharmacology of a BID schedule may support future combination studies with other drugs that are administered BID.

Evaluation of dexamethasone as a combination partner for ACP-196 builds on known antineoplastic activity of this drug in patients with MM. Dexamethasone therapy is commonly coadministered with targeted agents for MM (Ocio 2014). The dosing regimen of 40 mg weekly to be used in this study has been established based on randomized trial data showing the superiority of this method of administration (Rajkumar 2009). Combined use of ACP-196 and dexamethasone provides an all oral, noncytotoxic regimen that may have increased efficacy relative to administration of the individual agents alone. While dexamethasone can increase CYP3A4 activity and thus might enhance ACP-196 metabolism, it is considered a weak inducer of this isoenzyme and has not substantially altered the disposition of other CYP3A4 substrates (eg, bortezomib) that are commonly used in the therapy of MM (Hellmann 2011). The
randomized design of this pilot study will allow the potential for drug-drug interactions between ACP-196 and dexamethasone to be assessed.

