5.5.4 Analysis of Pharmacokinetic/Pharmacodynamic Parameters

The plasma PK of ACP-196 and dexamethasone will be characterized using noncompartmental analysis. The following PK parameters will be calculated, whenever possible, from plasma concentrations of ACP-196:

Product: ACP-196 (acalabrutinib) Date: 13 January 2016 Protocol: ACE-MY-001

- AUC_{0-t} Area under the plasma concentration-time curve calculated using linear trapezoidal summation from time 0 to time t, where t is the time of the last measurable concentration (C_t).
- AUC₀₋₁₂ Area under the plasma concentration-time curve from 0 to 12 hours, calculated using linear trapezoidal summation.
- AUC_{0- ∞} Area under the plasma concentration-time curve from 0 to infinity, calculated using the formula: AUC_{0- ∞} = AUC_{0-t} + C_t / λ_z , where λ_z is the apparent terminal elimination rate constant.
- $AUC_{0-24calc}$ Area under the plasma concentration-time curve from 0 to 24 hours, calculated by doubling the value for AUC_{0-12} .
- C_{max} Maximum observed plasma concentration
- T_{max} Time of the maximum plasma concentration (obtained without interpolation)
- t_{1/2} Terminal elimination half-life (whenever possible)
- λ_z Terminal elimination rate constant (whenever possible)
- CL/F Oral clearance

Missing dates or times may be imputed for PK and PD samples if the missing values can be established with an acceptable level of accuracy based on other information obtained during the visit in question. If PK and PD sampling for a given subject is not performed according to protocol instructions that subject may be excluded from the PK and PD analyses.

The PK parameters will be tabulated and summarized using descriptive statistics.

For each PD variable, the concentration at each assessment will be described. The change from baseline to each assessment will be summarized. The best change from baseline during the study will also be summarized. As appropriate, the on-treatment values will be compared with the pretreatment baseline values using paired t-tests.

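### The design can assess only dexamethasone's effect on ACP-196, not the reverse, and for that one direction these documents specify a table with no ratio or interval.

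*Protocol*

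**What the plan says.** Protocol Section 3.3 notes that dexamethasone could raise CYP3A4 activity and so speed ACP-196 metabolism, judges this a weak effect, and then says that the "randomized design of this pilot study will allow the potential for drug-drug interactions between ACP-196 and dexamethasone to be assessed".

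The regimens in Section 3.1 are "Cohort 1: ACP-196 100 mg BID continuously" and "Cohort 2: ACP-196 100 mg BID continuously and 40 mg dexamethasone once weekly". On size: "Forty subjects will be randomized 1:1 into the following 2 cohorts to receive ACP-196". Cohort 1 subjects may later have dexamethasone added, but always to continuing ACP-196 (Sections 3.1 and 3.5.5.1).

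The PK objective in Section 2.2 covers ACP-196 with and without dexamethasone but, for the partner drug, only the "PK profile of dexamethasone with concomitant ACP-196 administration".

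Section 5.5.4 applies noncompartmental analysis to both drugs and then lists parameters for one: "The following PK parameters will be calculated, whenever possible, from plasma concentrations of ACP-196". The analysis is one sentence: "The PK parameters will be tabulated and summarized using descriptive statistics". Section 5.2 says the study was not formally designed to compare the regimens. SAP Sections 1 and 4.3 refer PK to separate reports, and SAP Section 5 tests no formal hypotheses.

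**The concern.** The Section 3.3 sentence speaks of interactions between the two drugs, which reads as both directions. An effect of one drug on another needs the affected drug measured with and without the other. The trial has that contrast for ACP-196 and lacks it for dexamethasone.

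For ACP-196 the contrast exists, but what these documents specify is summaries by cohort. Two columns of means and standard deviations do not show how large a difference the data leave open. The question is not idle. Section 1.3.1 reports that a strong CYP3A inhibitor raised ACP-196 AUC about 5-fold, so the pathway matters to exposure. Section 3.3 calls dexamethasone a weak CYP3A4 inducer, while the label reproduced in Appendix 4 (legible in the Amendment 1 copy) calls it moderate. If similar columns were read as reassurance, a loss of ACP-196 exposure could pass into later combination work with no bound on its size.

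**Working it through.** **The plan's own figure.** The only power statement concerns ORR: 69% for 15% against 40%, n = 19, one-sided 0.025, exact binomial. It reproduces. The smallest r with P(X ≥ r | 19, 0.15) ≤ 0.025 is 7 (exact level 0.0163), and P(X ≥ 7 | 19, 0.40) = 0.692. It says nothing about PK, and no precision figure for the interaction question is given.

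**Which direction has a comparator.**
- Dexamethasone's effect on ACP-196: ACP-196 is measured alone in Cohort 1 and with dexamethasone in Cohort 2, by random allocation. Estimable.
- ACP-196's effect on dexamethasone: dexamethasone is measured only in subjects who also take ACP-196, from Day 1, swallowed at the same time (Sections 3.5.3.2 and 3.5.4). There is no ACP-196-free arm, period or sample. Not estimable, whatever a PK plan says.

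**Precision for the estimable direction.** Inputs are from Protocol Table 1-4 (Day 8, CLL, sampling to 6 h) at 100 mg: BID AUC 837 ± 485 (N = 22), QD AUC 634 ± 197 (N = 7), BID Cmax 716 ± 658 (N = 22). Carrying these over to myeloma is an assumption.

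Formulas: CV = SD/mean; log-SD s = √ln(1 + CV²); SE of the log ratio = s·√(2/n); 90% CI around an observed ratio of 1 = exp(± t(0.95, 2n − 2)·SE). Power for a true ratio of 0.70 is from the noncentral t, two-sided 5%, noncentrality |ln 0.70|/SE = 0.357/SE.

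With n = 20 per cohort, t = 1.686:
- BID AUC: CV = 485/837 = 0.579; s = 0.538; SE = 0.538 × √0.1 = 0.170; exp(± 0.287) = 0.75 to 1.33; noncentrality 2.10, power 53%.
- QD AUC: CV = 197/634 = 0.311; s = 0.304; SE = 0.096; exp(± 0.162) = 0.85 to 1.18; noncentrality 3.72, power 95%.
- BID Cmax: CV = 658/716 = 0.919; s = 0.782; SE = 0.247; exp(± 0.417) = 0.66 to 1.52; noncentrality 1.44, power 29%.

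The 31% CV is the lowest AUC value in the table. The other QD rows give 789/1240 = 64%, 1180/2170 = 54% and 1040/1870 = 56%.

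**Effect of early closure.** SAP Section 3.1 says enrolment stopped in March 2016; cohort sizes reached are not given. Assuming 10 per cohort for illustration (t = 1.734), the AUC interval becomes 0.66 to 1.52 at CV 58% (power for a 30% fall 29%) or 0.79 to 1.27 at CV 31% (power 70%).

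**Whether Day 1 can serve as a baseline.** Table 4-1 takes full profiles on Cycle 1 Days 1 and 22. Cohort 2 takes dexamethasone with ACP-196 in clinic on Day 1, and the post-dose samples follow at 0.5 to 6 h. Day 1 AUC is therefore already on dexamethasone in one arm. Adjusting for it could absorb an immediate interaction, leaving only the additional effect of repeated dosing.

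**The case against.** The best defence is that Section 3.3 has one direction in mind. Its preceding sentence concerns only dexamethasone's effect on ACP-196, and the randomised cohorts address exactly that. Section 1.2.5 calls ACP-196 unlikely to cause CYP interactions, and the objective promises only a dexamethasone profile. This stands in part. The design does have the property for one direction, and a reader who inferred that no interaction at all can be assessed would be wrong. The sentence still claims more than the design gives.

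Second, the study is a pilot with descriptive aims. A reader might infer that the sponsor plans to conclude there is no interaction. No document says so; that is a risk of misreading, not a stated plan.

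Third, PK is deferred. The SAP points to separate reports, the Amendment 1 summary mentions a separate PK/PD analysis plan, and Section 5.5.5 allows further PK analyses. A ratio with an interval may be specified there. So the finding is that none appears in these documents, not that none is planned. The deferral cannot help the other direction, which lacks data rather than analysis.

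Fourth, the precision depends on variability borrowed from another disease. That is fair, and it is why a range is shown. At the low end a 30% fall in AUC would usually be detected.

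Fifth, one might ask for an equivalence margin. None is given in the documents, and a descriptive pilot does not need one.

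**Conclusion.** The point holds in limited form. The Section 3.3 statement is right for dexamethasone's effect on ACP-196 and unsupported for ACP-196's effect on dexamethasone. For the supported direction, these documents provide tabulation without an estimate of the difference or its uncertainty.

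On the protocol's own variability, with 20 per cohort, an observed AUC ratio of 1 would be compatible with true ratios from about 0.75 to 1.33, or from 0.85 to 1.18 at the lowest CV. Cmax is less precise. No PK test is planned, so the power figures only indicate what a side-by-side reading could overlook. All of this assumes that CLL variability applies and that the planned cohort sizes were reached; early closure would widen the intervals. Similar-looking summaries cannot by themselves exclude a moderate interaction. This is a secondary objective and the safety analysis is unaffected, but the change is worth making because the claim is explicit and the remedy is cheap.

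**What to change.** - In Section 3.3, limit the sentence to the effect of dexamethasone on ACP-196, and state that dexamethasone PK is descriptive with no ACP-196-free reference. If the protocol will not be reissued, put the statement in the PK report.
- In Section 5.5.4 or the PK report, give the Cohort 2/Cohort 1 geometric mean ratio of ACP-196 AUC0-t and Cmax at Cycle 1 Day 22 with a 90% CI, not adjusted for Day 1, presented as an estimate.
- State that absence of an interaction will not be concluded from the summary table alone. No equivalence margin is required.
- A Day 1-adjusted ratio may be added as a supportive analysis of repeated dosing, labelled as such, because the Cohort 2 Day 1 post-dose samples follow the first dexamethasone dose.

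Cost: one sentence of rationale and two ratios in the PK report, from samples already scheduled. Downside: the report will probably have to say that a moderate interaction was not excluded.
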